4.2 Exclusion criteria

1. Involvement in the planning and/or conduct of the study (applies to both AstraZeneca staff and/or staff at the study site).
2. Previous enrollment in the present study.
3. Participation in another clinical study with an investigational product (IP) during the last 4 weeks.
4. Concurrent enrollment in another clinical study unless it is an observational (non-interventional) clinical study or the follow-up period of an interventional study.
5. Major surgical procedure (as defined by the Investigator) within 28 days prior to the first dose of IP. Note: Local surgery of isolated lesions for palliative intent is acceptable where this does not affect assessment of target lesions.
6. Any condition that, in the opinion of the Investigator, would interfere with the evaluation of the IP or interpretation of patient safety or study results, including but not limited to ongoing or active infection, symptomatic congestive heart failure, uncontrolled hypertension, unstable angina pectoris, cardiac arrhythmia, or psychiatric illness/social situations that would limit compliance with study requirement, substantially increase risk of incurring AEs from the study medications, or compromise the ability of the patient to give written informed consent.
7. Radiation therapy to the chest and whole-brain irradiation must be completed at least 4 weeks prior to start of study treatment, and patients must have recovered from any acute adverse effects prior to start of study treatment. An exception to this is palliative radiotherapy for bone lesions and must be completed before the first dose of study treatment.
8. Past medical history of interstitial lung disease, drug-induced pneumonitis, radiation pneumonitis that required steroid treatment, or any evidence of clinically active interstitial lung disease.
9. Patient has an inability to swallow oral medications. Note: Patient may not have a percutaneous endoscopic gastrostomy tube or be receiving total parenteral nutrition.
10. Prior exposure to any WEE1 inhibitors.
11. Any known hypersensitivity or contraindication to the components of the study drugs, AZD1775 and CBDP, or drugs with a similar chemical structure or class to the study drugs.
12. History of hypersensitivity to active or inactive excipients of any investigational drug in the study those investigated in the study.

13. Patient has had prescription or non-prescription drugs or other products known to be sensitive to cytochrome P450 (CYP)3A4 substrates or CYP3A4 substrates with a narrow therapeutic index, or to be moderate to strong inhibitors/inducers of CYP3A4 which cannot be discontinued 2 weeks prior to the first day of study drug dosing and withheld throughout the study until 2 weeks after the last dose of study drug. Coadministration of aprepitant or fosaprepitant during this study is prohibited. The use of sensitive substrates of CYP3A4, such as atorvastatin, simvastatin and lovastatin, is also prohibited in this study. As grapefruit and Seville oranges are known to contain moderate inhibitors of CYP3A4, these fruits or their products (including marmalade, juice, etc.) should be avoided while taking AZD1775. (see Appendix I Disallowed Medications and Medications to be Administered with Caution). Transporter studies (in vitro) have shown that AZD1775 is an inhibitor of breast cancer resistance protein (BRCP). The use of rosuvastatin in this study is prohibited.
14. Herbal preparations are not allowed throughout the study. These herbal medications include but are not limited to: St. John's wort, kava, ephedra (ma hung), ginkgo biloba, dehydroepiandrosterone (DHEA), yohimbe, saw palmetto and ginseng. Patients should stop using these herbal medications 7 days prior to first dose of study treatment.
15. Patients with Grade ≥ 2 neuropathy will be evaluated on a case-by-case basis after consultation with AstraZeneca Study Physician.
16. Patient with mean resting corrected QT interval (specifically QTc calculated using the Fridericia formula) > 470 msec from 3 ECGs performed within 5 minutes apart at study entry or congenital long QT syndrome.
17. Any of the following cardiac diseases currently or within the last 6 months as defined by New York Heart Association \geq Class 2 ([Appendix B1 New York Heart Association Criteria](#))
18.).
 - Unstable angina pectoris
 - Congestive heart failure
 - Acute myocardial infarction
 - Conduction abnormality not controlled with pacemaker or medication
 - Significant ventricular or supraventricular arrhythmias (patients with chronic rate-controlled atrial fibrillation in the absence of other cardiac abnormalities are eligible)
18. AZD1775 should not be given to patients who have a history of Torsades de pointes unless all risk factors that contributed to Torsades have been corrected (see Section

4.5.2 AZD1775 has not been studied in patients with ventricular arrhythmias or recent myocardial infarction.

19. History of another primary malignancy except for:

- Malignancy treated with curative intent and with no known active disease ≥ 5 years before the first dose of study drug and of low potential risk for recurrence
- Adequately treated non-melanoma skin cancer or lentigo maligna without evidence of disease
- Adequately treated carcinoma in situ without evidence of disease (eg, cervical cancer in situ)

20. History of leptomeningeal carcinomatosis.

21. Spinal cord compression unless asymptomatic or treated and stable off steroids and anti-convulsants for at least 1 month prior to study treatment.

22. Female patients who are pregnant or breastfeeding.

4.3 Patient enrollment and randomization

See Section 4.3 of the master protocol.

4.3.1 Procedures for handling incorrectly enrolled or randomized patients

See Section 4.4 of the master protocol.

4.4 Methods for assigning treatment groups

Not Applicable.

4.5 Restrictions

Please refer to Section 4.6 of the master protocol for details of the restrictions that apply to all patients in the study. Restrictions specific to Arm B include:

AZD1775 should be taken with 8 ounces of water approximately 2 hours before or 2 hours after food.

If BID dosing and a patient misses one of the two daily doses according to schedule, the dose should be taken as soon as possible, but not more than 6 hours after the missed dose was scheduled. If greater than 6 hours, the missed dose should be skipped and the patient should take the next dose when scheduled.

If vomiting occurs after a patient takes the AZD1775 dose, the patient should be instructed not to retake the dose, but to wait until the next scheduled dose of AZD1775. If no dose is scheduled for the following day, the dose will not be ‘made up’. If vomiting persists, the patient should contact the Investigator.

4.5.1 Women of childbearing potential

Women of childbearing potential (WoCBP) may be included only if acceptable contraception is in place for 2 weeks before commencing study treatment, for the duration of the study, and for 6 months after the last dose of study drug.

WoCBP is defined as women between menarche and menopause who have not been permanently or surgically sterilized and are capable of procreation.

All WoCBP must have a negative pregnancy test during screening and within 3 days prior to starting each treatment cycle.

Male patients who are involved in the study must agree to avoid procreative and unprotected sex (ie, using acceptable forms of contraception as described in [Appendix G](#)) and must not donate sperm during the study and for 6 months after the last dose of study drug. Where the female partner is pregnant or not using effective birth control, men should be advised to abstain while in the study and for 6 months after the last dose of study drug.

Female partners, who are of childbearing potential, of men participating in the study will also be required to use effective contraceptive measures (detailed in [Appendix G](#)) while their partner is on study drug and for 6 months thereafter.

Because of the possibility of irreversible infertility due to therapy with carboplatin, male patients will be advised to arrange for the freezing of sperm samples prior to the start of the study should they wish to father children at a future date.

4.5.2 Patients with a history of Torsades de pointes

AZD1775 should not be given to patients who have a history of Torsades de pointes unless all risk factors that contributed to Torsades have been corrected. AZD1775 has not been studied in patients with ventricular arrhythmias or recent myocardial infarction. See appendix I for a list of drugs that can cause Torsades de pointes.

4.6 Discontinuation of investigational product

See Section [4.9](#) of the master protocol.

4.7 Criteria for withdrawal

See Section [4.10](#) of the master protocol.

4.8 Discontinuation of the study

See Section [4.11](#) of the master protocol.

5. STUDY PLAN AND TIMING OF PROCEDURES

The procedures for the screening and the treatment periods in this study are presented in [Appendix B Table 1](#).

Appendix B Table 1 Schedule of assessments for AZD1775 + Carboplatin combination therapy

		AZD1775 and Carboplatin (cycle 21 days)									FOLLOW UP		For details see
	Screening	Cycle 1				Cycle 2		Cycle 3 and beyond			End of study treatment visit (30 days FU) ± 2 days	Every 2 months (± 2 weeks)	
Assesment	Baseline (-28 to -1)	Day 1	Day 3	Day 8	Day 15	Day 1 (± 2 days)	Day 8 (± 2 days)	Day 1 (± 2 days)	Day 3	Day 8 (± 2 days)			
Informed consent: study procedures including biomarker sample collection ^a	X												Section 6 of the master protocol
Study Procedures													
Physical examination (full)	X	X				X		X			X		Section 6.2.2 of master protocol
Vital signs ^b	X	X				X		X			X		Section 6.2.4 of master protocol
ECG ^c	X	X				X		X					Section 6.2.3 of master protocol
Concomitant medications	X	X				X		X			X		Section 8.7 of master protocol

Appendix B Table 1 Schedule of assessments for AZD1775 + Carboplatin combination therapy

		AZD1775 and Carboplatin (cycle 21 days)									FOLLOW UP		For details see
	Screening	Cycle 1				Cycle 2		Cycle 3 and beyond			End of study treatment visit (30 days FU) ± 2 days	Every 2 months (± 2 weeks)	
Assesment	Baseline (-28 to -1)	Day 1	Day 3	Day 8	Day 15	Day 1 (± 2 days)	Day 8 (± 2 days)	Day 1 (± 2 days)	Day 3	Day 8 (± 2 days)			
Demography, including baseline characteristics and tobacco use	X												Section 6 of master protocol
Eligibility criteria	X												Sections 4.1 and 4.2 of master protocol and Appendix B sections 5.1 and 5.2
Laboratory assesments													
Clinical chemistry	X	X ^d		X	X	X	X	X		X	X		Table 2 Appendix B
Hematology	X	X ^d		X	X	X ^e	X	X ^e		X	X		Table 3 Appendix B
Hepatitis B and C and HIV	X												
Urinalysis	X	as clinically indicated										Table 4 Appendix B	

Appendix B Table 1 Schedule of assessments for AZD1775 + Carboplatin combination therapy

		AZD1775 and Carboplatin (cycle 21 days)										FOLLOW UP		For details see
	Screening	Cycle 1				Cycle 2		Cycle 3 and beyond				End of study treatment visit (30 days FU) ± 2 days	Every 2 months (± 2 weeks)	
Assesment	Baseline (-28 to -1)	Day 1	Day 3	Day 8	Day 15	Day 1 (± 2 days)	Day 8 (± 2 days)	Day 1 (± 2 days)	Day 3	Day 8 (± 2 days)				
Coagulation (PT/INR/PTT)	X	as clinically indicated												Table 2 appendix B
Pregnancy test	X	X				X		X						Section 6.2.1 of master protocol
Pharmacokinetics														
AZD1775 PK sample (plasma)			X ^g						X ^g					Section 6.4 of master protocol and Appendix B Table
CBDP PK sample (plasma)		X ^h						X ^h						Section 6.4 of master protocol and Appendix B Table
Monitoring														
WHO/ECOG performance status	X	X				X		X				X		Section 6.3.1 of master protocol

Appendix B Table 1 Schedule of assessments for AZD1775 + Carboplatin combination therapy

		AZD1775 and Carboplatin (cycle 21 days)									FOLLOW UP		For details see
	Screening	Cycle 1				Cycle 2		Cycle 3 and beyond			End of study treatment visit (30 days FU) ± 2 days	Every 2 months (± 2 weeks)	
Assesment	Baseline (-28 to -1)	Day 1	Day 3	Day 8	Day 15	Day 1 (± 2 days)	Day 8 (± 2 days)	Day 1 (± 2 days)	Day 3	Day 8 (± 2 days)			
AE/SAE assessment ⁱ	X	X	X	X	X	X	X	X	X	X	X	X ^s	Section 7 of master protocol
IP Administration													
CBDP, ^{m, k}		X				X		X					Section 8.1.2 of Appendix B
Dispense AZD1775 Review/Collect Dosing Diary ^{j, l, n}		X				X		X					Section 8.1.1 of Appendix B
Study laboratory assessments													
mRNA		X											Section 6.6.1.4 of master protocol
CCI		X				X					X		Section 6.6.1.2 of

Appendix B Table 1 Schedule of assessments for AZD1775 + Carboplatin combination therapy

		AZD1775 and Carboplatin (cycle 21 days)									FOLLOW UP		For details see
	Screening	Cycle 1				Cycle 2		Cycle 3 and beyond			End of study treatment visit (30 days FU) ± 2 days	Every 2 months (± 2 weeks)	
Assesment	Baseline (-28 to -1)	Day 1	Day 3	Day 8	Day 15	Day 1 (± 2 days)	Day 8 (± 2 days)	Day 1 (± 2 days)	Day 3	Day 8 (± 2 days)			
													master protocol
Tumor biopsy (newly acquired or archival ≤3 years old) ^{ar}	X												Section 6.6.1.2 of master protocol
Tumor evaluation (CT or MRI) (RECIST 1.1) ^{o, p}	X	q6w ± 1 week (relative to the date of first dose) until confirmed objective disease progression/death (whichever comes first).										Section 6.1 of master protocol	
Subsequent anticancer therapy recording in eCRF												X	n/a
Survival status												X ^s	Section 6.1.1 of master protocol

^a If laboratory or imaging procedures were performed for other reasons prior to signing consent, these can be used for screening purposes with consent of the patient. However, all screening laboratory and imaging results must have been obtained within 28 days of enrollment.

^b Body weight is recorded along with vital signs.

- ^c ECG is mandatory on Day 1 of each Cycle and could be done at other visits if clinically indicated. Any clinically significant abnormalities detected require triplicate ECG results.
- ^d If screening laboratory assessments are performed within 3 days prior to Day 1 (first infusion day), they do not need to be repeated at Day 1. Serum or plasma chemistry, coagulation, hematology, and/or LFT monitoring may be performed more frequently if clinically indicated.
- ^e Haematology results must be available prior to dosing of each cycle, and reviewed by the treating physician or Investigator according to the dose modification and safety management guidelines in Section 7.3
- ^f For women of childbearing potential only. A urine or serum pregnancy test is acceptable. Women of childbearing potential are required to have a pregnancy test within 3 days prior to the first dose of study drug and then every 4 weeks. Pregnancy test may occur on Day 1, but results must be available and reviewed by the treating physician or Investigator prior to commencing an infusion
- ^g Predose and C_{max} 2-4 hours post dose day 3 for alternate cycles starting from C1.
- ^h Up to 60 minutes pre-dose and end of infusion, for alternate cycles starting from C. Pre-dose PK sample should be taken prior to the dosing of any study drug .
- ⁱ For AEs/SAEs reported during screening, additional information such as medical history and concomitant medications may be needed.
- ^j Five doses of AZD1775 (225 mg PO BID) will be taken in approximate 12-hour intervals over 2.5 days (Days 1-3). AZD1775 should be taken approximately 2 hours before or 2 hours after food.
- ^k Results for serum or plasma chemistry and LFT monitoring must be available before commencing administration (within 3 days) and reviewed by the treating physician or Investigator prior to dosing.
- ^l All patients must take a 5-HT3 antagonist prior to each dose of AZD1775, for example, ondansetron (ZOFTRAN[®]) 8 mg PO BID or granisetron (KYTRIL[®]) 1 mg PO BID. The 5-HT3 antagonist may be given by IV if necessary.
- ^m Carboplatin AUC 5 IV will be administered according to institutional standards on Day 1 of each 21-day cycle after AZD1775 dosing.
- ⁿ Review AZD1775 dosing compliance with the patient at the beginning of each new treatment cycle when study drug is dispensed.
- ^o RECIST 1.1 assessments will be performed on images from CT (preferred) or MRI, each preferably with IV contrast of the chest, abdomen (including liver and adrenal glands), and pelvis every 6 weeks (+/- 1 week). Pelvic imaging is recommended only when primary or metastatic disease in the pelvic region is likely. Additional anatomy should be imaged based on signs and symptoms of individual patients at baseline and follow-up. Baseline assessments should be performed no more than 28 days before the date of enrollment and, ideally, should be performed as close as possible to and prior to the start of the initial dose of IP.
- ^p Patients will have scans done q6w for the first 48 weeks, and then q12w thereafter (relative to the date of first IP administration) until objective disease progression.
- ^r If available patient's newly acquired or archival ≤ 3 years old tumor samples should be collected. Should there be no sample available no new biopsy is needed to be obtained.
- ^s Following treatment discontinuation, assessments for survival and SAE/AE must be made monthly for the first 3 months and then every 2 months thereafter.

Note: All assessments on treatment days are to be performed prior to infusion, unless otherwise indicated.

AE Adverse event; C Cycle; CT Computed tomography; ECG Electrocardiogram; ECOG Eastern Cooperative Oncology Group;
HIV Human immunodeficiency virus; IM Intramuscular; INR International normalized ratio; IP Investigational Product; LFT Liver function

Clinical Study Protocol Appendix B

Drug Substance Durvalumab (MED14736), tremelimumab, AZD1775, carboplatin, olaparib, ceralasertib (AZD6738)

Study Code D419QC00002

Version 05

Date 16Jan2020

test; MRI Magnetic resonance imaging; PD Progressive disease; PK Pharmacokinetic; PT Prothrombin time; PTT Partial thromboplastin time; q6w Every 6 weeks q8w Every 8 weeks; q12w Every 12 weeks; RECIST 1.1 Response Evaluation Criteria in Solid Tumors; SAE Serious adverse event; T₃ Triiodothyronine; T₄ Thyroxine; TSH Thyroidstimulating- hormone; WHO World health Organization.

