5. STUDY PLAN AND TIMING OF PROCEDURES

The study plan for each arm of the study will be included in the appropriate arm appendix. Please consult the appendix for the sub-study in which patients are enrolled (eg, [Appendix A](#) for Arm A). See [Figure 2](#) for the study flow chart.

For all treatment arms

- Tumor efficacy (RECIST) assessment dates are not affected by dose delays and remain as originally scheduled, as they are based on the date of initiation of study therapy.
- All other scheduled assessments must be performed relative to the start of the dosing cycle such that all laboratory procedures, etc required for dosing should be performed within 3 days prior to dosing. See individual arm appendix for details of all scheduled assessments.

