6.2 Safety assessments

6.2.1 Laboratory safety assessments

Blood and urine samples for determination of clinical chemistry, hematology, and urinalysis will be taken at the times indicated in the study plan (see the specific section of the relevant arm appendix). Please also refer to the Laboratory Manual.

Clinical laboratory safety tests, including serum pregnancy tests, will be performed in a licensed clinical laboratory according to local standard procedures. Sample tubes and sample sizes may vary depending on the laboratory method used and routine practice at the site. Pregnancy tests may be performed at the site using a licensed test (urine or serum pregnancy test). Clinically significant abnormal laboratory results should be repeated as soon as possible (preferably within 24 to 48 hours).

Additional safety samples may be collected if clinically indicated at the discretion of the Investigator. The date, time of collection, and results (values, units, and reference ranges) will be recorded on the appropriate eCRF.

Laboratory tests do not need to be repeated at baseline if the baseline visit is within 3 days of the screening sample. The date of each collection will be recorded in the appropriate eCRF.

The laboratory variables to be measured are presented in the relevant appendix (eg, [Appendix A](#) for Arm A).

Additionally, a urine/serum sample will be collected from all women of childbearing potential at screening and before the first dose for a pregnancy test in all combination arms.

If a patient shows an aspartate aminotransferase (AST) **or** alanine aminotransferase (ALT) $\geq 3\times$ upper limit of normal (ULN) **or** total bilirubin $\geq 2\times$ ULN, refer to [Appendix E](#) for further instructions on cases of increases in liver biochemistry and evaluation of Hy's Law. These cases should be reported as SAEs if, after evaluation, they meet the criteria for a Hy's Law case or if any of the individual liver test parameters fulfil any of the SAE criteria.

Any clinically significant abnormal laboratory values should be repeated as clinically indicated and recorded on the eCRF. Situations in which laboratory safety results should be reported as AEs are described in [Section 7.3.7](#).

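### Arm B's pregnancy-test footnote lets a Day 1 result wait until the infusion, which follows oral AZD1775, and sets a 4-weekly repeat against a 21-day cycle; both clash with Appendix B Section 4.5.1

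*Protocol*

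**What the plan says.** Three places in the protocol govern pregnancy testing in Arm B.

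- **Appendix B Section 4.5.1** states that all women of childbearing potential "must have a negative pregnancy test during screening and within 3 days prior to starting each treatment cycle".
- **Appendix B Table 1, grid.** Under the header "AZD1775 and Carboplatin (cycle 21 days", the pregnancy-test row marks screening and Day 1 of Cycle 1, of Cycle 2, and of Cycle 3 and beyond. For details the row points to "Section 6.2.1 of master protocol". That section says only that "a urine/serum sample will be collected from all women of childbearing potential at screening and before the first dose for a pregnancy test".
- **Appendix B Table 1, footnote f** has the same patients "required to have a pregnancy test within 3 days prior to the first dose of study drug and then every 4 weeks". It allows the test on Day 1, in which case the "results must be available and reviewed by the treating physician or Investigator prior to commencing an infusion".

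The dosing order is fixed twice. Footnote m of the table and the text under Appendix B Figure 2 both put oral AZD1775 first and the carboplatin infusion second. Master protocol Section 5 adds, for all arms, that "all laboratory procedures, etc required for dosing should be performed within 3 days prior to dosing".

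**The concern.** Footnote f ties two things to the wrong reference point for this arm.

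The first is when the result must be known. The footnote holds back only the infusion. In Arm B the cycle starts with an oral drug, so a site working from the table could dispense AZD1775, see it taken, and read the result before starting carboplatin. The footnote does not say that the result must be negative either.

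The second is how often the test is repeated. A 4-week interval drifts against a 21-day cycle and contradicts both the grid and Section 4.5.1.

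What is at stake is fetal exposure. Pregnancy excludes a patient from Arm B (Appendix B Section 4.2, criterion 22) and stops treatment at once if it occurs (Appendix B Section 7.2.1). Master protocol Section 7.7 exempts from reporting only a pregnancy found before any study drug is received. A result read between AZD1775 and carboplatin therefore turns an unexposed case into an exposed and reportable one, which pre-dose testing is meant to prevent.

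**Working it through.** **Result review: the wording side by side**

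| Place | Point by which the result is needed |
|---|---|
| Appendix B 4.5.1 | negative test within 3 days before each cycle starts |
| Table 1 footnote f (pregnancy) | before an infusion |
| Table 1 footnote e (haematology) | "Haematology results must be available prior to dosing of each cycle" |
| Table 1 footnote h (carboplatin PK) | before any study drug |
| Table 1 footnote k (chemistry, liver tests) | before administration |
| Table 1 grid | marks the day of the test; says nothing about the result |
| Table 1 closing note | before infusion |
| Master 6.2.1 | sample at screening and before the first dose; says nothing about the result |

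Carboplatin follows AZD1775, so before an infusion is later than before dosing. The grid, the closing note and Master 6.2.1 do not close that gap.

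**Likely origin.** Appendix A Table 2 footnote f carries the same sentences, with 7 days in place of 3 for the first test. They fit Arm A, where both drugs are infused every 4 weeks. Footnote k was also carried over from Arm A, and there the reference to an infusion was changed to administration. Footnote f had its 7 days changed to 3, but not its infusion wording or its interval. Arm C (Appendix C Table 3, footnote d) ties the repeat test to Day 1 of each cycle.

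**Interval: calendar check**

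Inputs: cycle length 21 days (Table 1 header); repeat interval 28 days (footnote f); coverage window 3 days (Section 4.5.1).

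- Start of cycle k: 1 + 21(k − 1), giving Days 1, 22, 43, 64, 85.
- Test j under footnote f: 1 + 28(j − 1), giving Days 1, 29, 57, 85.
- A start is covered if a test falls 0 to 3 days before it.

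| Cycle | Start | Latest 4-weekly test | Gap (days) | Covered |
|---|---|---|---|---|
| 1 | Day 1 | Day 1 | 0 | yes |
| 2 | Day 22 | Day 1 | 21 | no |
| 3 | Day 43 | Day 29 | 14 | no |
| 4 | Day 64 | Day 57 | 7 | no |
| 5 | Day 85 | Day 85 | 0 | yes |

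The pattern repeats every 84 days (4 × 21 = 3 × 28). Coverage is 1 start in 4, or 3 of the first 12 (Cycles 1, 5 and 9). Moving Day 1 within the table's ±2 days does not help: the smallest gap among Cycles 2 to 4 becomes 7 − 2 = 5 days, still more than 3.

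In Days 1 to 84 the grid gives 4 tests and the footnote gives 3, with only Day 1 in common. The footnote's Day 29 is Cycle 2 Day 8 (22 + 7) and Day 57 is Cycle 3 Day 15 (43 + 14). The grid marks no pregnancy test on either.

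Testing before each 21-day cycle covers 12 of 12 starts.

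**The case against.** The best defence concerns the review point. Footnote f sets a condition on the infusion and nowhere expressly permits AZD1775 with a result outstanding. Section 4.5.1 is unconditional, and AZD1775 on Day 1 starts the cycle, so a pending result already breaches it. A site can satisfy both rules, and the stricter governs. Footnote d also labels Day 1 as the first infusion day, which suggests that infusion is used loosely for Day 1 dosing. For Cycle 1, inclusion criterion 11 and Master Section 4.3 already bar treatment without post-menopausal status or a negative test. On the interval, the grid and Section 4.5.1 agree with each other, so two of the three sources are right.

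Much of this stands. The correct rule exists and is mandatory. The review wording is weaker than Section 4.5.1 rather than an explicit licence to break it. The interval error bites only at a site that puts the footnote above both the grid and Section 4.5.1.

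The loose reading of infusion does not stand. Footnote d only names the day, while footnotes e, h and k of the same table use dosing, study drug or administration where something must be settled before treatment. The eligibility safeguards can be met by a screening test and do not reach later cycles. Finally, the pregnancy-test row sends the reader to Master Section 6.2.1, which does not lead on to Section 4.5.1.

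**Conclusion.** The concern holds. Followed as written, footnote f gives a weaker safeguard than Section 4.5.1 on the timing of the result, in any cycle where the test is done on Day 1. Its interval contradicts the 21-day cycle, the grid and Section 4.5.1.

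The size is minor. The number of women of childbearing potential in Arm B is not given; the arm takes up to 20 patients (Appendix B Section 2.6), or up to 40 if expanded under the master protocol. The coverage of 3 in 12 cycle starts assumes that a site follows the footnote instead of the grid, with tests counted from Day 1 and no cycle delays. A site that follows the grid loses nothing on frequency, and one that follows Section 4.5.1 loses nothing at all. Objective response rate and the analysis baseline are not affected.

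**What to change.** In Appendix B Table 1, footnote f:

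1. Replace the 4-weekly repeat with a test within 3 days before Day 1 of each 21-day cycle.
2. Require the result to be available, reviewed and negative before the first dose of any study drug in that cycle, naming AZD1775, instead of before an infusion.

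In the pregnancy-test row, add Appendix B Section 4.5.1 beside the reference to Master Section 6.2.1. As optional tidying, change the table's closing note from infusion to dosing, as in Arm C.

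The cost is two phrases and one cross-reference. No visit or test is added, because the grid already places a pregnancy test on Day 1 of every cycle.
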